5 ANALYSIS POPULATIONS (ANALYSIS SETS)

Since this is an OLE with patients from the primary study, all patients will be included in a single Full Analysis Set for reporting.

6 CONVENTION FOR REPORTING TREATMENT PERIODS

Periods III and IV: The protocol defines Period III as a 12 month period when patients are in three specific dose groups, and Period IV as starting on 0.66 mg/kg/week after 12 months in Period III. Because of the differences in timing of transition to the 0.66 mg/kg/week dose, all data from Periods III and IV will be presented in 12 month intervals, starting with the first dose of treatment at the start of Period III. The dose at the beginning of each 12 month period will be used to classify the patient to a dose group for disposition purposes. For the first 12 months, the results will be reported by the assigned dose group. After the initial year on OLE, all patient results will be summarized in a single treatment group, regardless of assigned dose level, or any individual patient dose adjustments.

Period V: This period will contain data from patients on PEN treatment. Baseline data for this period will be the data collected at the visit for the first PEN dose, prior to the first PEN dose.

The cumulative change in HT SDS from the start of treatment in Period I will also be summarized. For these summaries, the original dosing assignment will be used, and the reporting periods will be at each of the scheduled Month 12 visit of the period. Gaps in treatment will be included, so that the elapsed time may be longer than 12 months.

7 STATISTICAL ANALYSIS METHODS

7.1 Statistical Methods

This is an open label long-term extension study. No formal hypothesis testing will be performed. Descriptive statistics will include mean, median, standard deviation, minimum, maximum, range, count and confidence intervals to present the results. All output will be created with SAS version 9.4 or higher.

7.2 Interim Analysis

Not applicable.

7.3 Adjustment for Clinical Center

The analysis will not be stratified by study site.

7.4 Data Handling and Missing Data

Because of the observational nature of this study, missing data in general will not be imputed, except for:

1. specific items associated with AEs as specified in Section 9.1;

2. missing day or month will be imputed to the 1st of each if needed for calculations, unless this imputation contradicts a previous date (such as between start and stop dates). In this case, the imputed date will be last day or month, or be missing and presented as "ongoing."

Unscheduled assessments or multiple results within a specified visit window will be listed, but not used in the visit summary. The assessment closest to the scheduled visit date will be used.

Early termination assessments will be assigned to the appropriate annual interval based on treatment month within a period.

7.5 Issues of Laboratory Data

If there were two or more evaluable results in a given visit, the latest test result will be used for analysis. If the evaluable result was indicated by <nn, half of the value (= nn/2) will be used for the summary. If the evaluable result was >nn, the value (= nn) will be used for the summary.

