9.4 IGF-1 and IGF-1 SDS

IGF-1 will be listed for each patient, but not summarized. IGF-1 SDS will be listed, and summarized at each visit. In addition, the number and proportion of patients with IGF-1 SDS > 2 will be summarized. The denominator will be the number of patients with results at each visit. For the summaries of each 12 month period with multiple visits, each patient will be counted once, and will be counted as having IGF-1 SDS >2 if any results within that summarized interval is >2. IGF-1 SDS will also be summarized by ADA status.

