9.6 Laboratory Test Results

Clinical laboratory measurements will be summarized with descriptive statistics at each visit. Changes within each 12 month period will use the first visit of the 12 month period as the baseline. For Period V the baseline will be the first visit with PEN injection. If data from the first visit of each period are not available, the last previous visit data will be used. Summary of abnormal results (reported as low, high, clinically significant) will be provided for each 12 month period, with the number of patients at the beginning of each period for the denominator.

The following laboratory results will be presented:

Glucose Metabolism	Endocrinology	Lipid Metabolism
Fasting blood Glucose	FT4	Cholesterol
Fasting Insulin	Т3	High density lipoprotein (HDL)
HbA1c	Thyrotropin (= TSH)	Low density lipoprotein (LDL) Cholesterol
	Cortisol, Free	Lipoprotein-A
	Females >=12 y.o.: FSH, LH and estradiol	Triglycerides
	Male >=13 y.o.: FSH, LH and testosterone	

Glucose Metabolism, Endocrinology, and Lipid Metabolism:

Clinical Chemistry	Hematology	Urinalysis
Albumin	Differential Blood Count of Leukocytes	Bilirubin
Alkaline phosphatase	Erythrocyte Count	Glucose
Calcium	Hematocrit	Ketones
Chloride	Hemoglobin	Leukocyte Esterase
Creatinine	Leukocytes	Nitrite
Gamma-glutamyl Transferase (GGT)	Mean Corpuscular Hemoglobin (MCH)	рН
Lactate Dehydrogenase (LDH)	Mean Corpuscular Hemoglobin Concentration (MCHC)	Protein
Phosphate	Mean Corpuscular Volume (MCV)	Specific Gravity
Potassium	Platelet Count	Urinalysis Blood
Serum Glutamic Oxaloacetic Transaminase (SGOT)		Urobilinogen
Serum Glutamic Pyruvic Transaminase (SGPT)		
Serum Iron and Transferrin		
Sodium		
Total Bilirubin		
Total Proteins		
Urea (blood urea nitrogen)		
Uric Acid		

• Chemistry, Hematology, and Urinalysis:

The increases in alanine aminotransferase (ALT), aspartate aminotransferase (AST), and total bilirubin will be examined for liver function. The count and percentage of the increases will be tabulated for each visit including baseline. The increases of ALT and AST will be examined in three categories, i.e. $>2 \times$ upper limit of normal (ULN), $>3 \times$ ULN, and $>5 \times$ ULN, and that of total bilirubin combined with ALT or AST increases will be examined in 1 category, total bilirubin $>3 \times$ ULN and ALT or AST $>2 \times$ ULN.

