14.5.5.2	Laboratory Test Abnormal Results – Hematology: Full Analysis Set
14.5.6.1	Laboratory Test Results – Urinalysis: Full Analysis Set
14.5.6.2	Laboratory Test Abnormal Results – Urinalysis: Full Analysis Set
14.5.7	Laboratory Test Results – Increases in ALT, AST, and Total Bilirubin: Full Analysis Set
14.6.1	Vital Signs by Visit and Change from Start of OLE: Full Analysis Set
14.6.2	Physical Examination Abnormalities by Visit: Full Analysis Set
14.6.3.1	ECG Results by Visit and Change Within Each Year: Full Analysis Set
14.6.3.2	Electrocardiogram (ECG) Abnormal Shifts by Year: Full Analysis Set
14.6.4	Concomitant Medications Within Each Year by ATC2 and Preferred Term: Full Analysis Set
14.7.1	Total Duration of Treatment: Full Analysis Set
3.1.1	Summary of treatment emergent adverse event (All causality) by SOC and PT (Safety Analysis Set)
6.1.1	Summary of treatment-emergent adverse events leading to study drug withdrawn (All Causalities) (Safety Analysis Set)
6.1.2	Summary of treatment-emergent adverse events leading to study drug reduction or interruption (All Causalities) (Safety Analysis Set)
6.1.3	Summary of treatment-emergent adverse events leading to study discontinuation (All Causalities) (Safety Analysis Set)
OC15.4	Annual Incidence and Severity of Treatment-Emergent Adverse Events by SOC and Preferred Term: Full Analysis Set
OC15.6	Annual Incidence and Relationship of Treatment-Emergent Adverse Events by SOC and Preferred Term: Full Analysis Set

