11.3 Figures

Figure No.	Description
7	Height SDS and Cumulative Change in Height SDS by Year and by ADA Status in Study (All Cohorts Combined)
8	IGF-1 SDS by Year by ADA Status in Study
14.2.1.1&2	Annualized Height Velocity
14.2.1.3	Summary of Annualized Height Velocity for All Cohorts Combined at Each Year of Study
14.2.2.2A	Summary of Height SDS by Initial Cohort Assignment at Each Year of Study
14.2.2.2B	Summary of Height SDS by Year of Study and Initial Cohort Assignment
14.2.2.2C	Summary of Height SDS for All Cohorts Combined at Each Year of Study
14.3.5.1	IGF-1 SDS
14.4.2.1&2	Annualized Height Velocity by ADA Status
14.4.2.3	Summary of Annualized Height Velocity for All Cohorts Combined at Each Year of Study by ADA Status
14.4.2.5&8	Summary of Height SDS for All Cohorts Combined at Each Year of Study by ADA Status
14.4.2.9	Peak IGF-1 SDS by ADA Status
14.5.1.1	Clinical Laboratory Summary: Glucose Metabolism
14.5.2.1	Clinical Laboratory Summary: Endocrinology

Figure No.	Description
14.5.3.1	Clinical Laboratory Summary: Lipid Profile
14.5.4.1	Clinical Laboratory Summary: Chemistry
14.5.5.1	Clinical Laboratory Summary: Hematology
14.5.6.1	Clinical Laboratory Summary: Urinalysis
16.2.8.7	Maximum Bilirubin Versus Maximum ALT and AST

Signature Page for CP-4-004 OLE SAP v6.0

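### SAP 7.4 and 7.5 pick among repeat laboratory results by different rules with no stated precedence, and on either reading the by-visit liver table can omit a real elevation

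*SAP*

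**What the plan says.** SAP 7.4 (data handling) gives a general rule: "Unscheduled assessments or multiple results within a specified visit window will be listed, but not used in the visit summary". It continues: "The assessment closest to the scheduled visit date will be used".

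SAP 7.5 (laboratory data) gives a different one: "If there were two or more evaluable results in a given visit, the latest test result will be used for analysis". Neither section refers to the other.

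SAP 9.6 then plans two kinds of laboratory count:

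- For ALT and AST above 2, 3 and 5 times ULN, and for the combined bilirubin criterion: "The count and percentage of the increases will be tabulated for each visit including baseline". This is Table 14.5.7, "Increases in ALT, AST, and Total Bilirubin: Full Analysis Set".
- For laboratory parameters generally: "Summary of abnormal results (reported as low, high, clinically significant) will be provided for each 12 month period", with patients at the start of the period as denominator. No ULN multiples are used here.

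SAP 11.3 also lists Figure 16.2.8.7, "Maximum Bilirubin Versus Maximum ALT and AST", by title only.

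For IGF-1, SAP 9.4 handles the same problem explicitly: in a 12-month summary a patient "will be counted as having IGF-1 SDS >2 if any results within that summarized interval is >2".

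**The concern.** Safety is the primary objective of this extension analysis (SAP 3.1.1), and Protocol 5.7.1 singles out liver enzymes for special attention. Repeat samples are foreseeable: Protocol 5.5.1 provides unscheduled visits to follow up, among other things, abnormal or alarming laboratory values. The record-selection rule therefore matters most when something has been found.

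Two things look wrong. First, two programmers following the SAP could select different records from the same data. Second, Table 14.5.7 takes one record per visit and has no worst-value or any-result rule. A value above a ULN threshold may then go uncounted in the one table built to count such values. Adverse event reporting does not fully close the gap. Under Protocol 7.1 an abnormal value is an adverse event only if it causes signs or symptoms, is judged clinically significant or needs therapy.

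**Working it through.** The plan gives no figure to reproduce. The check applies each rule to possible sample timings.

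**Inputs.** Selection rules: SAP 7.4 and 7.5. Table unit and thresholds: SAP 9.6. Visit window of ±2 weeks: for example Protocol 5.4.2. Patients starting the OLE: 53 (SAP 4.1). Assumed for illustration: one ALT result at 4 times ULN and one at 1 times ULN.

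**Step 1: the rules on four patterns.** Reading 1: 7.4 selects the visit date and 7.5 only settles repeats on that date. Reading 2: 7.5 overrides 7.4 for laboratory data. The question is whether the patient is counted as above 3 times ULN.

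| Pattern | Reading 1 | Reading 2 | Any-result rule |
|---|---|---|---|
| A: 4× on the planned date, 1× later in the window | counted | omitted | counted |
| B: 1× on the planned date, 4× later in the window | omitted | counted | counted |
| C: 4× earlier in the window, 1× on the planned date | omitted | omitted | counted |
| D: 4× at an unscheduled visit between windows, 1× on the planned date | omitted | omitted | counted |

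If both samples fall on the selected date, 4× first and 1× second, 7.5 takes the 1× result on either reading. So each reading can drop a real elevation, and C and D are dropped under both.

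**Step 2: is this an artefact of the patterns chosen?** Take every ordered pair of distinct days from −14 to +14, with one high and one normal result: 29 × 28 = 812 pairs. Remove the 28 pairs equally distant from the planned date, leaving 784. Compare the nearest-date rule with the latest-result rule:

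- they disagree in 50% (392 of 784);
- each omits the high value in 50% (392 of 784);
- both omit it in 25% (196 of 784).

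These shares enumerate possible timings. They are not expected frequencies.

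**Step 3: how many scheduled records feed the table.** Routine biochemistry per patient-year, from Protocol Appendices 2 to 5:

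- Period III: months 3, 6, 9 and 12 = 4 (former Genotropin patients also have Day 1 and Month 1).
- Period IV: month 12 = 1, plus the visit three months after a switch to 0.66 mg/kg/week for those who switch.
- First PEN year: PEN V1 and months 3, 6 and 12 = 4.
- Later PEN years: months 6 and 12 = 2.

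Patients returning after a treatment gap (before Period III or IV) and those terminating early have further samples. In a Period IV year without a switch, gap or termination, a single scheduled entry decides whether the by-visit table shows an elevation.

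**Step 4: scale.** 1/53 = 0.0189, so one patient is 1.9% at the OLE starting size.

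**The case against.** The best reply is that the two sections need not conflict: 7.4 deals with a visit window and 7.5 with results inside a visit, so they can be applied in sequence, or the laboratory-specific section can govern. This is fair, and one sentence would settle precedence. It does not remove the second problem, because Step 1 shows omissions on both readings.

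A second reply is that any table with one record per visit leaves values out, and that 7.4 openly says the rest are listed. That is also true. A by-visit table is a legitimate display. The gap is that no table counts patients by ULN multiple over a period.

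A third reply is that other outputs cover the gap. Chemistry results are listed (Listing 16.2.8.7). The maximum-value figure may show the elevation. The 12-month summary may too, since 7.4 restricts only visit summaries. Protocol 5.8 names liver enzymes at or above 2 times ULN among the guides for dose modification or interruption, and dose adjustments are summarised by reason (SAP 9.13). Adverse events leading to reduction or interruption have Table 6.1.2. These are real safeguards. However, the SAP does not define the records behind the figure or the 12-month summary, 7.5 speaks of analysis generally, and none of these outputs gives a count by ULN multiple.

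A reader might infer from Step 1 that each rule misses three elevations in four. The documents do not support that: the share follows from the patterns chosen. If D were instead high three days before the planned date and normal seven days after, the nearest-date rule would count two of four.

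**Conclusion.** The point holds as a defect in the specification of a safety table and should be corrected. Precedence between 7.4 and 7.5 is unstated, and the rules followed exactly can leave a real ALT or AST elevation out of Table 14.5.7 on either reading. This rests on the text alone: the table is by visit, one record is selected, and SAP 9.6 gives no any-result rule.

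The size of any understatement cannot be computed. The documents give neither how often tests are repeated nor how often values are raised, and the 1.9% only shows what one patient weighs. A reader might infer that elevations would disappear from the report, or that liver safety will be materially understated. Neither is supported: the values stay in the listings and may appear in the figure and the 12-month summary. The analysis is descriptive, so no test or error rate is affected.

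**What to change.** 1. In SAP 7.5, state one selection rule for by-visit laboratory descriptives, for example the nearest-date rule of 7.4, and say how ties and same-day repeats are resolved.
2. In SAP 9.6, keep Table 14.5.7 by visit. Add, for each 12-month period and for PEN, the number of patients with any post-baseline ALT or AST above 2, 3 and 5 times ULN, and with the existing combined bilirubin criterion on the same sampling date. Use all scheduled, unscheduled, repeat and early-termination results in the database. Protocol 5.5.1 allows a local laboratory at unscheduled visits, so classify each result against the ULN of the laboratory that reported it and identify local results. Show the number of patients with at least one result, and use the same records for Figure 16.2.8.7.
3. State that the 12-month abnormal-result summaries count a patient if any result in the period qualifies, as SAP 9.4 does for IGF-1 SDS above 2.

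The cost is SAP wording, one added summary and its derivation; no new data are collected. Counts may rise slightly, and patients sampled more often have more chances to be counted, which is why the number with at least one result should be shown.

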8 DEMOGRAPHICS, BASELINE CHARACTERISTICS AND STUDY SUMMARY

8.1 Patient Disposition

The number and percentage of patients entering and completing each 12 month period will be summarized by the dose level at the beginning of each period. A listing will be provided to show the reason for discontinuation and time of discontinuation for each patient.

Protocol deviations will be listed and summarized within each period, but will not be used to define patient groups.

8.2 Demographics

The demographics (age, gender, race) will be summarized using descriptive statistics at the start of Period III, and for each 12 month reporting period.

Age will be the age at the start of each reporting period, calculated from the date of day 1 of each period and the date of birth. If the date of birth is not available, then the age will be calculated from the elapsed months added to the age reported at the beginning of Period 1 of the study.

8.3 Weight, Height and BMI

Patient weight, HT, body mass index (BMI), HT SDS, IGF-1 SDS, BA, and HV will summarized at the start of OLE. Patient weight, HT and BMI will be summarized for each 12 month period. The patient's reported HT for each visit is the average of the three consecutive measurements made by study personnel. See Section 10.1 for details on HT outcomes.

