² Insulin tolerance test, with cortisol response to hypoglycemia if insulin stimulation test is chosen / Arginine test / Clonidine test / Glucagon test (plus or without propranolol) / L-dopa plus propranolol.

³ Central laboratory results will be used for eligibility confirmation.

OPKO Biologics	Protocol for Clinical Study CP-4-004	Page 42 of 133
Effective Date: Date of final electronic approval		

between two height measurements should be at least 6 months, but should not exceed 18 months prior to inclusion.

6. BMI must be within ± 2 SD of mean BMI for the chronological age and sex according to the 2000 CDC standards (www.cdc.gov/growthcharts).
7. Baseline IGF-I level of at least 1 SD below the mean IGF-I level standardized for age and sex (IGF-I SDS ≤ -1.0) according to the central laboratory reference values.
8. Children with normal fundoscopy (ophthalmoscopy) at screening (without signs/symptoms of intracranial hypertension as assessed by fundoscopy).
9. Children with multiple hormonal deficiencies must be on stable replacement therapies for other hypothalamo-pituitary-organ axes for at least 3 months and 6 months for thyroid replacement therapy prior to the first study drug administration.
10. Normal 46 XX karyotype for girls.
11. Written informed consent of the parent or legal guardian of the patient and assent of the patient for the Main Study and for the OLE.

Patients who completed the first year of treatment in the Main Study are allowed to enter the OLE. Patients who were off treatment for over [REDACTED] after completing the main study (or during the OLE) are allowed to participate/continue in the OLE after completing additional testing.

Specific inclusion criteria for Period V (LT-OLE –PEN):

12. Continuing participation in the LT-OLE-PEN period.
13. Signed consent and assent (when applicable) form for the LT-OLE-PEN period.
14. Investigator's assessment and confirmation of the patient anticipated compliance to the protocol procedures.
15. Agreement to refrain from sexual activity during the study i.e. observe complete sexual abstinence as the only acceptable contraceptive measure in this study.

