4.2 EXCLUSION CRITERIA

1. Children with past or present intracranial tumor growth as confirmed by an MRI scan (with contrast).
2. History of radiation therapy or chemotherapy.
3. Malnourished children defined as:
 - a. Serum albumin below the lower limit of normal (LLN) according to the reference ranges of central laboratory, AND
 - b. Serum iron below the lower limit of normal (LLN) according to the reference ranges of central laboratory, AND
 - c. BMI < -2 SD for age and sex.
4. Children with psychosocial dwarfism.

OPKO Biologics	Protocol for Clinical Study CP-4-004	Page 43 of 133
Effective Date: Date of final electronic approval		

5. Children born small for gestational age (SGA = birth weight and/or birth length < -2 SD for gestational age).
6. Presence of anti-hGH antibodies at screening.
7. Any clinically significant abnormality likely to affect growth or the ability to evaluate growth, such as, but not limited to, chronic diseases like renal insufficiency, spinal cord irradiation, etc.
8. Patients with diabetes mellitus.
9. Patients with impaired fasting sugar (based on WHO; fasting blood sugar >110 mg/dl or 6.1 mmol/l after repeated blood analysis).
10. Chromosomal abnormalities and medical “syndromes” (Turner’s syndrome, Laron syndrome, Noonan syndrome, Prader-Willi Syndrome, Russell-Silver Syndrome, SHOX mutations/deletions and skeletal dysplasias), with the exception of septo-optic dysplasia.
11. Closed epiphyses.
12. Concomitant administration of other treatments that may have an effect on growth such as anabolic steroids and methylphenidate for attention deficit hyperactivity disorder (ADHD), with the exception of hormone replacement therapies (thyroxin, hydrocortisone, desmopressin (DDAVP)).
13. Children requiring glucocorticoid therapy (e.g. asthma) that are taking a dose of greater than 400 µg/d of inhaled budesonide or equivalents¹ for longer than 1 month during a calendar year.
14. Major medical conditions and/or presence of contraindication to r-hGH treatment.
15. Known or suspected HIV-positive patient, or patient with advanced diseases such as AIDS or tuberculosis.
16. Drug, substance, or alcohol abuse.
17. Known hypersensitivity to the components of study medication.
18. Other causes of short stature such as coeliac disease, hypothyroidism and rickets.
19. The patient and/or the parent/legal guardian are likely to be non-compliant in respect to study conduct.

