5.7.1.2 Assessment of glucose metabolism

Impaired glucose metabolism may lead to the discontinuation of study treatment. Glucose metabolism will be assessed through fasting insulin, fasting glucose levels and HbA1C levels.

Fasting glucose, insulin, and HbA1C will be assessed according to the schedule provided in [Appendix 1: Schedule of Assessments – Main Study](#) to [Appendix 5](#).

Safety monitoring of potentially impaired glucose metabolism will also include parameters that have been associated with insulin resistance (e.g., fasting lipid profiles, changes in blood pressure, weight and BMI).

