11 LIST OF TABLES AND DATA LISTINGS

11.1 Tables

Table No.	Description
2.1	Overall Summary of patients with treatment-emergent adverse events (Safety Analysis Set)
3.1	Summary of treatment emergent adverse event (All causality) in >= 2% of patients (Safety Analysis Set)
3.1b	Summary of treatment emergent adverse event (All causality) in >= 5% of patients (Safety Analysis Set)
4	Summary of Somatrogon Patient Disposition - CP-4-004 OLE
4.1	Summary of AESI - CP-4-004 OLE (Safety Analysis Set)
5.1	Summary of treatment-emergent serious adverse events (All Causalities) (Safety Analysis Set)
6	Summary of Antibody Titers Overall and by Year: Full Analysis Set
10	Annualized Height Velocity at End of each OLE and PEN Year by ADA Status: Full Analysis Set
11	Highest IGF-1 SDS During OLE and PEN Years by ADA Status: Full Analysis Set

Table No.	Description
20	Adverse Events of Special Interest in PEN Years: Full Analysis Set
1.2.2	Height SDS at Baseline and End of Main Study, End of OLE and PEN Years by Initial Cohort Assignment: Full Analysis Set
1.2.2.1	Cumulative Change in Height SDS at End of Main Study, End of OLE and PEN Years by Initial Cohort Assignment: Full Analysis Set
1.2.3	Highest IGF-1 SDS During OLE and PEN Years: Full Analysis Set
14.1.1.1	Disposition of Patients – Year 1 OLE
14.1.1.2	Disposition of Patients – OLE Years 2-4 and PEN
14.1.2.1	Demographics at Start of OLE (Year 1): Full Analysis Set
14.1.2.2	Demographics at Start of Years 2-4 and PEN: Full Analysis Set
14.1.3	Medical History at Start of Main Study: Full Analysis Set
14.1.4.1	Characteristics at Start of OLE (Year 1): Full Analysis Set
14.1.4.2	Weight, Height, and BMI at Start of OLE Years 2-4 and PEN Years: Full Analysis Set
14.2.1.1	Annualized Height Velocity at End of OLE Years: Full Analysis Set
14.2.1.2	Annualized Height Velocity on PEN: Full Analysis Set
14.2.1.3	Annualized Height Velocity (cm/yr) at End of Main Study, End of each OLE and PEN Year by Initial Cohort Assignment: Full Analysis Set
14.2.2.1	Height SDS at End of OLE and PEN Years: Full Analysis Set
14.2.2.2	Height SDS at Baseline and End of Main Study, End of each OLE and PEN Year by Initial Cohort Assignment: Full Analysis Set
14.2.3.1	Annual Change in Height SDS at End of each OLE Year: Full Analysis Set
14.2.3.2	Annual Change in Height SDS at End of each PEN Year: Full Analysis Set

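### Yearly BMI is summarised without age and sex standardisation and without change, so its trend in growing children is confounded with normal ageing

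*SAP*

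**What the plan says.** Protocol 5.7.1.2 says that safety monitoring of potentially impaired glucose metabolism will also cover parameters linked to insulin resistance, and gives as examples "fasting lipid profiles, changes in blood pressure, weight and BMI".

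SAP 8.3 covers BMI in two sentences. At the start of the extension: "Patient weight, HT, body mass index (BMI), HT SDS, IGF-1 SDS, BA, and HV will summarized at the start of OLE". After that: "Patient weight, HT and BMI will be summarized for each 12 month period". Height and IGF-1 carry the suffix SDS in the first sentence; BMI does not.

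In SAP 11.1 the matching outputs are Table 14.1.4.1 (characteristics at the start of OLE year 1) and Table 14.1.4.2, titled "Weight, Height, and BMI at Start of OLE Years 2-4 and PEN Years: Full Analysis Set". SAP sections 8 to 11 list no BMI SDS, BMI change or BMI abnormality output.

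The protocol does standardise BMI for eligibility. Inclusion criterion 6 requires BMI within 2 "SD of mean BMI for the chronological age and sex according to the 2000 CDC standards", and exclusion criterion 3c uses "BMI < -2 SD for age and sex".

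**The concern.** The protocol gives change in BMI a supportive safety purpose, but the SAP plans only yearly values on what appears to be the raw scale. Children enter at 3 years up to 10 (girls) or 11 (boys), spend 12 months in the Main Study, and are then followed through OLE years 1 to 4 and the PEN years. The daily comparator ends with the Main Study, and under SAP section 6 results after OLE year 1 are summarised in a single group. Time on drug, age and puberty therefore advance together.

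A reader who sees mean BMI rise from one year start to the next could not say how much is ordinary growth. The masking can also run the other way. Protocol 5.7.1.3 notes that GH reduces body fat stores, and a fall relative to age could be hidden by a rise in the raw mean.

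**Working it through.** The plan states no BMI figure, so there is nothing to reproduce. The check has two parts.

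**1. Texts compared**

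| Item | Protocol use | SAP extension analysis |
|---|---|---|
| Blood pressure | Named in 5.7.1.2 | 9.8: by visit, with change from start of OLE and within each year |
| Lipids | Named in 5.7.1.2 | 9.6: by visit, with change within each 12-month period and abnormal results |
| BMI | Named in 5.7.1.2; standardised in 4.1 and 4.2 | 8.3: values at OLE start and by year; no SDS, no change |
| Height | Standardised (5.6) | 8.3 and 10.3: HT SDS, with change |

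The SAP prints no unit for BMI. That it means raw BMI is an inference from the plain term beside HT SDS and IGF-1 SDS, and from the absence of any BMI SDS output.

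**2. Illustration of size (slopes and SDs are assumptions)**

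Intervals: Table 14.1.4.2 reports year starts. From OLE start to the start of Year 4 is three yearly intervals. A fourth is reached only if a child completes four OLE years before PEN, and SAP section 4 says that the timing of the PEN switch varies.

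Expected rise in mean raw BMI with BMI SDS unchanged = assumed slope × number of intervals.

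- Slope 0.3 kg/m2 per year: 0.3 × 3 = 0.9; 0.3 × 4 = 1.2.
- Slope 0.6 kg/m2 per year: 0.6 × 3 = 1.8; 0.6 × 4 = 2.4.
- Wider range, 0.2 to 0.8 per year: 0.2 × 3 = 0.6 to 0.8 × 3 = 2.4 over three intervals; 0.2 × 4 = 0.8 to 0.8 × 4 = 3.2 over four.

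Raw size of a true shift = SDS shift × assumed SD. For a gain of 0.5 SDS:

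- SD 1.5: 0.5 × 1.5 = 0.75 kg/m2.
- SD 2: 0.5 × 2 = 1.0 kg/m2.
- SD 3: 0.5 × 3 = 1.5 kg/m2.

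The shift (0.75 to 1.5) overlaps the ageing range and can be smaller than it.

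Sampling error for comparison: 95% half-width of a mean = 1.96 × SD / √n, with n = 53, the number who started the OLE (SAP 4.1).

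- SD 1.5: 1.96 × 1.5 / 7.28 = 0.40 kg/m2.
- SD 3: 1.96 × 3 / 7.28 = 0.81 kg/m2.

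These widths grow as patients leave. Over most of the assumed slopes the ageing component is larger than the sampling error, so more patients would not resolve the ambiguity. On the SDS scale a child who tracks the reference has an expected drift of zero.

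**The case against.** The strongest reply is that the SAP never offers these tables as safety evidence. Section 8.3 sits under demographics and baseline characteristics, where raw weight, height and BMI are ordinary descriptors of who enters each year, and age is summarised for the same periods (8.2). BMI is absent from the safety endpoint lists in protocol 2.2 and SAP 3.2.1. Protocol 5.7.1.2 mentions it only within a list of examples, which can be read as monitoring during the trial and not as a commitment to a group trend analysis. All of this stands, and it makes the point a small one.

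A reader might infer that a metabolic safety signal could pass undetected. The documents do not support that. Fasting glucose, insulin, HbA1c and lipids are summarised by visit with change and abnormal results (SAP 9.6), blood pressure is summarised with change (9.8), and glucose metabolism impairment is an adverse event of special interest (9.1). Nor is information lost: weight and height at each visit are in Listing 16.2.9.9.

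A reader might also infer that BMI SDS would isolate a drug effect. It would not. It removes the reference population's age trend, but catch-up growth, pubertal timing and GH effects on body fat remain mixed in a single uncontrolled group.

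What the reply leaves untouched is that the protocol speaks of changes in BMI, the SAP reports none, and the scale apparently chosen is the one on which change is hardest to interpret.

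**Conclusion.** The point holds as a minor improvement. As planned, the yearly BMI summary cannot separate a departure from normal growth from growth itself, because the values appear unstandardised, no change is reported, and the later years have one pooled group. On an assumed slope of 0.3 to 0.6 kg/m2 per year, ageing alone would move the mean by about 0.9 to 1.8 kg/m2 over three intervals or 1.2 to 2.4 over four. The size is illustrative only, since neither document gives a slope or an SD for BMI, and the reading of BMI as raw is inferred. The limitation is confined to the BMI summary. It does not touch a listed endpoint, bias another analysis or leave metabolic safety unassessed.

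**What to change.** In SAP 8.3 and Tables 14.1.4.1 and 14.1.4.2, add BMI SDS by the 2000 CDC standards, the reference in inclusion criterion 6, at OLE start and at each OLE and PEN year, with change from OLE start. Keep raw BMI beside it, and state the scale of each. Add a note that BMI SDS is to be read alongside pubertal status (SAP 10.5), because standardising does not supply a control group.

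The variable derives from height, weight, age and sex already collected, so no visit, measurement or clinical rule changes and the analysis stays descriptive. The cost is minor programming and one footnote: BMI would be standardised to CDC while height is standardised to the Prader reference (protocol 5.6), so the two scores rest on different populations.
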